### **Objective:**

The primary objective is to demonstrate non-inferiority of the detection rate of clinically significant prostate cancer in targeted biopsies based on PCaVision imaging (PCaVision pathway) in comparison with the detection rate of clinically significant cancer in targeted biopsies based on MRI (MRI pathway). In this comparison, clinically significant prostate cancer is defined as International Society of Urological Pathology (ISUP) Grade Group (GG)  $\geq 2$  in any of the biopsy cores taken from a lesion.

Secondary objectives are (1) to compare the proportion of men in whom targeted biopsies could be “safely” omitted in the PCaVision pathway, defined as the number of men in whom no lesions for target biopsies have been identified by PCaVision while no clinically significant cancer is detected in either MRI targeted biopsies or possible systematic biopsies, compared to the MRI pathway, (2) to perform the same diagnostic assessments described in the Primary objective for different definitions of the target condition, including (i) ISUP  $\geq 3$  in any of the biopsy cores taken from a lesion; (ii) ISUP  $\geq 2$  with cribriform growth and/or intraductal carcinoma (CR/IDC) in any of the biopsy cores taken from a lesion; (iii) ISUP = 1, (3) to compare the number of men in whom the PCaVision pathway provided insufficient quality images with the number of men with insufficient quality MRI images

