### Secondary Objectives

- To compare the proportion of men in whom targeted biopsies could be safely omitted in the PCaVision pathway versus the MRI pathway. This is defined as the number of men in whom no lesions for target biopsies have been identified by PCaVision while no clinically significant cancer is detected in either MRI targeted biopsies or systematic biopsies. The combined findings of all types of biopsies will serve as the reference standard to define 'safe'.
- To perform the same diagnostic accuracy analyses as described in the primary objectives for different definitions of the target condition. This includes: (i)  $ISUP \geq 3$  in any of the biopsy cores taken from a lesion; (ii)  $ISUP \geq 2$  with cribriform growth and/or intraductal carcinoma (CR/IDC) in any of the biopsy cores taken from a lesion; (iii)  $ISUP = 1$ .
- To compare the number of men in whom the PCaVision pathway generated insufficient quality images with the number of men with insufficient quality MRI images in the MRI pathway.
- To perform the same diagnostic accuracy analyses as described in the primary and secondary outcome with different levels of increased criteria for ultrasound image quality, automatically detected by PCaVision

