#### **4.5. Sample size calculation**

The sample size calculation is based on demonstrating non-inferiority between the detection rate of clinically significant cancer from the PCaVision pathway and the MRI pathway using patients as the unit of analysis and data from the fully paired design.

The detection rates of PCa (GG $\geq$ 2) based on MRI and PCaVision targeted biopsies are expected to be around 30%. These values are based on the detection rates of PCa (GG $\geq$ 2) reported by Mannaerts et al., 2020 [30] and Grey et al., 2022 [43], which were found to be 29% and 30% with MRI and 28% and 26% with 2D CUDI (older version of PCaVision), respectively.

The non-inferiority margin is set to 5% absolute difference in detection rate. The expected proportion of discordant pairs is 10%. This proportion expresses the degree in which PCaVision and MRI disagree with respect to detecting and missing significant cancers in a paired design. This parameter is relevant when analysing data from a paired study design. A smaller percentage of discordant pairs will lower the required sample size. In the studies of Mannaerts et al., 2020 [30] and Grey et al., 2022 [43], the percentage discordant pairs were 10.1% and 8.9%, respectively.

Our assumptions of the sample size calculations are therefore the following: an expected detection rate of 30% for both imaging techniques, a non-inferiority margin of 5% points and a percentage discordance between both imaging techniques of 10%, a one-sided type 1 error of 2.5% (as recommended by the European Medicines Agency) and a power of 80%. This leads to a required total sample size of 350 patients.. This is the total number of men who need to undergo both PCaVision and MRI, and produce images of sufficient quality, followed by targeted biopsies if indicated. This sample size calculation was performed according to Liu et al., 2002 [47] and Hintze, 2008 [48].

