### **8.3.3 Biopsy procedure and histological examination**

An urologist will perform software-assisted fusion TBx or cognitive TBx based on the standard of care of each participating centre. For each imaging modality (e.g. MRI and 3D mpUS), a maximum of 2 lesion will be targeted. Each lesion will be sampled using 3 biopsy cores. In case both imaging techniques have identified lesions to be biopsied, the targeted biopsy procedures are performed in a randomized order to prevent potential bias.

The applied prostate biopsy method; transperineal will be selected based on the standard of care of each participating clinical centre.

Individual biopsy cores from targeted biopsies will be separately analysed by an uropathologist for the presence of PCa, ISUP, Gleason score (GS), percentage tumour core involvement and morphological patterns including cribriform growth pattern and intraductal carcinoma (CR/IDC) in accordance with the 2019 ISUP guidelines [34]. A work order instruction for the exact sample labelling of the biopsies and histopathological workup will be provided and agreed on with each clinical site.

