## 10. STATISTICAL ANALYSIS

In the analyses, we will compare the histological findings from two main diagnostic pathways: (1) PCaVision imaging in all men followed by targeted biopsies in men with suspicious lesions; (2) MRI imaging in all men followed by targeted biopsies in men with suspicious lesions. The findings will be analysed and reported at the per-patient rather than per-lesion level because the per-patient level of reporting has the greatest clinical relevance. In the analysis, we differentiate between the following two datasets:

- Total study population, all men included in the study to undergo PCaVision and MRI imaging.
- Paired dataset with sufficient quality images and subsequent targeted biopsies for both PCaVision and MRI.

The last dataset will be used in the paired analysis when comparing the diagnostic accuracy of different imaging pathways.

In the descriptive part of the analysis we will show the cross- tabulation of histological findings (ranging from no cancer, GG=1 to GG=5) comparing the two main diagnostic pathways: PCaVision based targeted biopsies against MRI based targeted biopsies.

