Furthermore, the same effect measures and statistical approach will be used as in the previous analyses, only the definition of the target condition will change. The following alternative definitions of the target condition (rather than  $ISUP \geq 2$ ) will be used: (i)  $ISUP \geq 3$ ; (ii)  $ISUP \geq 1$ ; (iii)  $ISUP = 1$ . The reason also assessing alternative definitions is that there is still ongoing discussion about the clinical relevance of these histological findings.

Both imaging techniques (PCaVision and MRI) can produce images of insufficient quality impeding the process of taking targeted biopsies. This hampers the clinical usefulness of the imaging technique in practice. Therefore, we will compare the proportion of men in whom the PCaVision pathway produces insufficient-quality images or targeted biopsies with the proportion of men with insufficient-quality MRI images or target biopsies in the MRI pathway. The same statistical approach for paired proportions will be used in the comparison of the detection rate.

The PCaVision software includes automated detection of ultrasound image quality by analysing patient motion and CEUS signal. We will analyse diagnostic accuracy of PCaVision using the same statistical approach with increased requirements of ultrasound images quality with regards to motion and CEUS signal. The exact levels of these increased requirements are described in section 6.1.2.

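### Section 10.2 lists ISUP ≥1 where the summary, section 2 and section 8.1.2 have ISUP ≥2 with cribriform/intraductal carcinoma, so the analysis chapter contradicts the stated secondary endpoint

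*Combined protocol and SAP*

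**What the plan says.** Section 2 (Secondary Objectives) sets the task: "To perform the same diagnostic accuracy analyses as described in the primary objectives for different definitions of the target condition". It then names three conditions. The second is ISUP ≥2 "with cribriform growth and/or intraductal carcinoma (CR/IDC) in any of the biopsy cores taken from a lesion". Section 8.1.2 gives the same three. The summary does too; after ISUP ≥2 its list reads "with cribriform growth and/or intraductal carcinoma (CR/IDC) in any of the biopsy cores taken from a lesion; (iii) ISUP = 1".

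Section 8.3.3 provides the data. The uropathologist examines each targeted core separately and reports, among other things, "morphological patterns including cribriform growth pattern and intraductal carcinoma (CR/IDC) in accordance with the 2019 ISUP guidelines".

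Section 10.2 is the part of the statistical chapter that should carry these definitions into the analysis. The sentence that starts "The following alternative definitions of the target condition (rather than" lists ISUP ≥3, ISUP ≥1 and ISUP = 1. The effect measures and methods are said to be those of the preceding analyses. The descriptive part of chapter 10 promises a "cross- tabulation of histological findings (ranging from no cancer, GG=1 to GG=5"), which is by grade group only.

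**The concern.** CR/IDC is the only alternative definition that adds morphology to grade. If section 10.2 is followed literally, the study will not compare how often the two pathways detect these cancers. It will report a comparison of any-cancer detection that no objective asks for. A reader who sets the endpoint list beside the results would see one endpoint gone and another added, and could not tell whether that was settled before or after the data were seen.

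There is also a procedural difficulty. Section 12.8 treats a departure from the statistical plan in the protocol as a protocol deviation. While the two lists differ, analysing CR/IDC departs from section 10.2, and omitting it departs from sections 2 and 8.1.2.

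**Working it through.** **The plan's own figure.** The nearest figure is the sample size in section 4.5. Its inputs are a margin of 0.05, discordance of 0.10, equal detection rates, one-sided 2.5% and 80% power. The score-type formula for paired proportions is n = ((z₀.₉₇₅·s₀ + z₀.₈₀·s₁)/0.05)².

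- s₁² = 0.10, so s₁ = 0.3162.
- The restricted estimates under the null are 0.0345 and 0.0845, so s₀² = 0.0345 + 0.0845 − 0.05² = 0.1165 and s₀ = 0.341 (0.3412 with unrounded estimates).
- n = ((1.960 × 0.3412 + 0.8416 × 0.3162)/0.05)² = 349.6, which rounds up to 350.
- 350 × 1.25 = 437.5, which rounds up to 438.

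Both stated figures reproduce. Neither uses an alternative target condition, so the point below changes neither.

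**The lists side by side.**

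| Place | (i) | (ii) | (iii) |
|---|---|---|---|
| Summary, Objective | ISUP ≥3 | ISUP ≥2 with CR/IDC | ISUP = 1 |
| Section 2, Secondary Objectives | ISUP ≥3 | ISUP ≥2 with CR/IDC | ISUP = 1 |
| Section 8.1.2 | ISUP ≥3 | ISUP ≥2 with CR/IDC | ISUP = 1 |
| Section 10.2 | ISUP ≥3 | **ISUP ≥1** | ISUP = 1 |

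Items (i) and (iii) agree in all four places. Item (ii) agrees in three and differs in the fourth.

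**Does anything else in chapter 10 cover CR/IDC?** No. The primary analysis uses GG ≥2 without morphology. The cross-tabulation is by grade group. The remaining secondary analyses concern safely omitted biopsies, image quality and stricter ultrasound quality thresholds.

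**Can CR/IDC be analysed as sections 2 and 8.1.2 ask?** Yes. The unit is the patient (section 8.1.1), the paired method is in section 10.1, and CR/IDC is recorded per core (section 8.3.3). Only the line in section 10.2 is wrong.

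**Is ISUP ≥1 already covered by the other analyses?** Only in part. Assume that each man is classed by his highest grade in each pathway. Then the detection rate for ISUP ≥1 equals the rate for ISUP = 1 plus the rate for ISUP ≥2, and the point differences add in the same way. The discordant pairs do not add. Take one man with GG1 on MRI-targeted cores and GG2 on PCaVision-targeted cores:

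| Target condition | MRI | PCaVision | Pair | PCaVision − MRI |
|---|---|---|---|---|
| ISUP = 1 | yes | no | discordant | −1 |
| ISUP ≥2 | no | yes | discordant | +1 |
| ISUP ≥1 | yes | yes | concordant | 0 |

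The differences sum correctly (−1 + 1 = 0). The discordant counts do not (1 + 1 = 2 against 0). Paired intervals and the McNemar test depend on discordance, so the inference for ISUP ≥1 cannot be read off the other two.

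**The case against.** The strongest reply is that this is one combined document, and that sections 2 and 8.1.2 do more than name CR/IDC: they call for the same accuracy analyses on it as on the primary endpoint. That stands. A reader might infer from section 10.2 that the CR/IDC objective has been abandoned, or that no analysis of it exists anywhere. The documents do not support this. The omission is confined to chapter 10, and the data and method are in place. Nor do they show whether ISUP ≥1 was put there on purpose or by slip.

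A reader might also infer that ISUP ≥1 is redundant and should be deleted or left untested. The worked example shows that it is not redundant for a paired comparison. The complaint that it includes insignificant cancers applies at least as much to ISUP = 1, which all four lists contain. Whether to keep an any-cancer analysis is the sponsor's choice, and nothing in the documents rules it out.

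It is tempting, too, to say that CR/IDC will be rare and its interval wide. The documents give no frequency. All that follows is that, as a subset of ISUP ≥2, its detection rate cannot exceed the rate for ISUP ≥2, which is expected to be about 30%.

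One defence fails. The mismatch is not an effect of text extraction. The heading of section 10.2 is garbled in the text, but the list itself is a complete numbered sentence, and one misread symbol would not account for the missing words on cribriform and intraductal growth.

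**Conclusion.** The point holds as an internal contradiction. Section 10.2 omits one of three pre-stated alternative target conditions and substitutes one that appears in no objective or endpoint. Chapter 10 has no CR/IDC analysis, while sections 2 and 8.1.2 require one.

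The consequence is limited to a secondary endpoint. The primary endpoint, the 5-point margin, the sample size and the data collection are unaffected, and the conflict can be fully corrected before analysis. The mismatch itself rests on no numerical assumption. The remark on ISUP ≥1 assumes that men are classed by highest grade per pathway. The precision of the CR/IDC comparison cannot be judged from the documents.

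**What to change.** In section 10.2, restore item (ii) as ISUP ≥2 "with cribriform growth and/or intraductal carcinoma (CR/IDC) in any of the biopsy cores taken from a lesion", so that it matches the summary and sections 2 and 8.1.2 word for word. For ISUP ≥1, choose one of two courses and record the choice before analysis: remove it from section 10.2, or, if it is intended, add it to sections 2 and 8.1.2 as a further secondary endpoint alongside CR/IDC.

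The cost is one line in section 10.2, plus a matching line in sections 2 and 8.1.2 if ISUP ≥1 is kept, handled under the amendment procedure in section 12.3. It needs no new data, patients or procedures, because CR/IDC is already recorded for each targeted core.

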#### 8.1.2 Secondary study parameters/endpoints

- proportion of men in whom targeted biopsies could have been safely omitted in the PCaVision pathway compared to the MRI pathway. This is defined as the number of men in whom no lesions for target biopsies have been identified by PCaVision while no clinically significant cancer is detected in either MRI targeted biopsies or systematic biopsies. The combined findings of all types of biopsies will serve as the reference standard to define 'safe'.
- same diagnostic accuracy analyses as described in the primary endpoint for different definitions of the target condition. This includes: (i) ISUP  $\geq 3$  in any of the biopsy cores taken from a lesion; (ii) ISUP  $\geq 2$  with cribriform growth and/or intraductal carcinoma (CR/IDC) in any of the biopsy cores taken from a lesion; (iii) ISUP = 1.
- comparison of the number of men in whom the PCaVision pathway provided insufficient quality images or targeted biopsies with the number of men with insufficient quality MRI images or target biopsies in the MRI pathway.
- same diagnostic accuracy analysis as described in the primary and secondary outcome but using increased ultrasound image quality requirements (predefined and automated in PCaVision)

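### The image-failure objective counts unusable images only, but its endpoint and analysis also count failed targeted biopsies, and no final image-only comparison is planned

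*Combined protocol and SAP*

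**What the plan says.** Two definitions stand in the current text.

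- **Images only.** The Secondary Objectives in section 2 read "To compare the number of men in whom the PCaVision pathway generated insufficient quality images with the number of men with insufficient quality MRI images". The Summary, under Objective, has the same content: the men "in whom the PCaVision pathway provided insufficient quality images with the number of men with insufficient quality MRI images".
- **Images or biopsies.** The secondary endpoint in 8.1.2 is worded more widely: "the PCaVision pathway provided insufficient quality images or targeted biopsies with the number of men with insufficient quality MRI images or target biopsies". The secondary endpoint analysis (10.2) repeats this as a proportion: "the PCaVision pathway produces insufficient-quality images or targeted biopsies with the proportion of men with insufficient-quality MRI images or target biopsies".

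The reason that 10.2 gives just before the analysis sentence is about images: "Both imaging techniques (PCaVision and MRI) can produce images of insufficient quality impeding the process of taking targeted biopsies".

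Elsewhere the plan treats the two causes of loss as distinct but excludes men for either. Section 4.5 allows for inadequate images and, separately, for technical problems in taking targeted biopsies. Section 8.4 excludes men for poor imaging or technical problems with ultrasound, MRI or biopsy. The paired dataset in section 10 requires both adequate images and the subsequent targeted biopsies. Section 6.1.2 gives numerical quality thresholds for ultrasound. We found no corresponding threshold for MRI, no criterion for an insufficient targeted biopsy, and no statement that the two components will be reported separately.

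**The concern.** How often each technique gives unusable images is a stated secondary objective. It also balances a primary analysis that is confined to men with adequate images and biopsies from both techniques: a method that fails often could still look non-inferior in the men who remain.

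The two definitions count different men. Under the composite, a man with good images and a failed biopsy counts as a failure of that technique. This can happen only if the technique marked a lesion, because without a lesion no targeted biopsy is taken (sections 5.1 and 8.2). The composite therefore mixes image quality with biopsy execution and with the rate at which lesions are marked. A real difference in unusable scans could be diluted or masked, and a difference in biopsy failure could be read as one in image quality. As 8.1.2 and 10.2 stand, no final paired result would separate these.

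**Working it through.** **Figures in the plan.** No rate, power or sample size is given for this endpoint. The enrolment figure used below does reproduce. With 10% discordant pairs, a 5-point margin, one-sided 2.5% and 80% power, the score-test formula gives (1.960 × √0.11642 + 0.8416 × √0.10)² / 0.05² = 349.6, so 350. Then 350 × 1.25 = 437.5, so 438. Neither figure depends on how image failure is defined.

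**Inputs for the illustration**

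- N = 438 (section 4.5), taken as all imaged with both techniques.
- Lesion-positive on MRI: (273 + 441) / 1000 = 0.714, from the counts per thousand men in section 1.
- Lesion-positive on ultrasound: 0.30 × 0.91 + 0.70 × (1 − 0.56) = 0.273 + 0.308 = 0.581. The accuracy comes from the earlier 82-patient CEUS study in section 1 and the prevalence from the MRI figures there. It is a stand-in, not a PCaVision figure.
- Image and biopsy failure rates: assumptions, since the documents give none by technique.
- Test: exact McNemar, two-sided 5%, also an assumption. The plan names McNemar for the comparison of safely omitted biopsies; for this endpoint 10.2 refers only to the paired approach used for detection rate.

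**Formulas.** For one technique, composite rate = i + (1 − i) × L × b, where i is image failure, L the lesion-positive proportion and b biopsy failure among men with a lesion. With composite rates P (PCaVision) and M (MRI) and independent failures, the discordant proportions are P(1 − M) and M(1 − P). Power is the exact binomial sum over the number and split of discordant pairs.

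**Worked case, b = 5% on both**

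- PCaVision: 0.10 + 0.90 × 0.581 × 0.05 = 0.126
- MRI: 0.05 + 0.95 × 0.714 × 0.05 = 0.084
- The difference shrinks from 5.0 to 4.2 points and the background of discordant pairs grows.

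**A true image difference (10% v 5%)**

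| Biopsy failure, PCaVision / MRI | Composite rates | Power |
|---|---|---|
| none (images only) | 10.0% v 5.0% | 78% |
| 1% / 1% | 10.5% v 5.7% | 72% |
| 2% / 2% | 11.0% v 6.4% | 66% |
| 5% / 5% | 12.6% v 8.4% | 49% |
| 2% / 6% | 11.0% v 9.1% | 14% |

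Simulating the same model moves these by about a point (73% and 50% in the 1% and 5% rows).

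**No image difference (5% v 5%)**

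- Images only: significant in about 3.5% of trials (the exact test is conservative).
- Biopsy failure 8% v 2%: composite 9.4% v 6.4%, significant in about 35%.
- Biopsy failure 2% v 1%: composite 6.1% v 5.7%, significant in about 4%.
- Biopsy failure 5% v 5%: composite 7.8% v 8.4%, significant in about 5%.

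**If biopsy failures are shared.** Suppose one 5% event per man affects every technique with a lesion, with lesion status independent between techniques and image failure 10% v 5%. The discordant proportions are then 0.0987 and 0.0565, and power is about 57% rather than 49%.

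**The case against.** The strongest reply is that the wider wording is deliberate and sensible. Section 5.1 treats imaging plus targeted biopsy as a package. Sections 4.5, 8.4 and 10 remove men for either kind of failure, so the composite counts the men lost from the primary comparison, and as a check on that loss it fits better than image failure alone. Sections 8.1.2 and 10.2 also agree with each other. All of this stands, and it is why the composite should be kept.

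The size is also open to challenge. The large effects need 5% biopsy failure or opposed rates, and nothing in the documents points to such gaps: one physician takes both sets of biopsies in a single visit, and section 7.1.5 calls for the same fusion system. If biopsy failures are rare, the two definitions give nearly the same answer. Failures shared by both techniques in one man are largely concordant and cost less power. Unequal lesion marking alone matters little: with equal image and biopsy failure of 5%, the composite is significant in about 5% of trials. These limits stand too.

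The interim analysis in 10.3 does look at discarded scans, but to revisit the sample size. It is not a final comparison between techniques.

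What the reply leaves untouched is that the objective, and the reason given in 10.2, are about images, and no planned final analysis isolates them.

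**Conclusion.** The mismatch is real and minor. Followed as written, the plan tests pathway failure and leaves its stated objective on image quality without an analysis of its own.

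A reader might infer that the composite is the wrong endpoint, or that it will seriously distort the comparison. The documents support neither. The composite matches the plan's exclusions, and the distortion depends on biopsy-failure rates that the documents do not give. Under the assumptions above, the loss of power runs from about 6 points (78% to 72%) at 1% failure on each technique to about 64 points (78% to 14%) at 2% v 6%. A false signal of any size needs a clear gap between techniques: about 35% at 8% v 2%, but only about 4% at 2% v 1%. The primary non-inferiority test, its margin, its alpha and the 350 and 438 men are unaffected.

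**What to change.** In 8.1.2 and 10.2:

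1. Add a paired comparison of insufficient-quality images alone, in all men imaged with both techniques, with the difference and a two-sided 95% confidence interval. Name it as the analysis that answers the objective in the Summary and section 2.
2. Keep the composite as a separate endpoint, named pathway failure (images or targeted biopsies).
3. Report targeted-biopsy failure as its own component for each technique, with men who had a lesion on that technique as the denominator.
4. State what makes an MRI or a targeted biopsy insufficient, and which paired test applies.

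The cost is one additional secondary comparison, a table line and some wording. Both reasons for loss must already be recorded to build the paired dataset, so no new data are needed.
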